4.5 Inclusion Criteria

1. Male and female treatment-seeking smokers who are between 18 and 65 years of age and self-report smoking at least 5 cigarettes (menthol and/or non-menthol) per day for at least the last 6 months.
2. Plan to live in the area for the duration of the study (i.e. ~30 weeks/8 months).
3. Capable of giving written informed consent, which includes compliance with the requirements and restrictions listed in the combined consent and HIPAA form.
4. Smokers who wish to make a permanent quit attempt in the next 1-2 months (treatment-seeking), because our prior work suggests that motivated subjects are more sensitive to medication effects on smoking behavior. Using a scale from 0 to 100 (100, being extremely interested), subjects must rate their interest in quitting smoking within the next 1-2 months greater than 50.
5. Able to communicate fluently in English (i.e. speaking, writing, and reading).
6. Participants will provide a Urine Cotinine sample that is present at a sensitivity of 100 ng/mL at the Intake Visit. If deemed safe by the Principle Investigator under federal and University guidelines, participants will provide a Carbon Monoxide (CO) breath test reading greater than or equal to 5 parts per million (ppm) at the Intake Visit

4.6 Exclusion Criteria

Subjects who present and/or self-report with the following criteria will not be eligible to participate in the study:

Smoking Behavior

1. Regular use of nicotine containing products other than cigarettes (e.g. chewing tobacco, snuff, snus, cigars, e-cigs, etc.). Participants agreeing to abstain from using nicotine containing products other than cigarettes and the study-provided TN for the duration of trial will be considered eligible.
2. Current enrollment or plans to enroll in another research and/or smoking cessation program over the duration of the study (i.e. ~30 weeks/8 months).
3. Anticipated use (within the next ~30 weeks/8 months) of any nicotine substitutes and/or smoking cessation treatments/medications unless provided through the study.
4. Participant who provide a Urine Sample that is absent of Cotinine at a sensitivity of 100 ng/mL at the Intake Visit. If deemed sage by the Principle Investigator under federal and University guidelines, if participants provide a CO breath test reading less than 5 ppm at Intake will not be eligible to participate in the study.

Alcohol and Drug

1. History of substance abuse (other than nicotine) in the past 12 months and/or currently receiving medical treatment for substance abuse. Counseling and support groups (e.g. Alcoholics Anonymous and Narcotics Anonymous) will not be considered medical treatment for the purposes of this protocol.
2. Current alcohol consumption that exceeds 25 standard drinks/week.
3. Breath alcohol reading (BrAC) greater than .000 at the Intake Visit for participants who complete an in-person consent. Participants who completed a virtual REDCap consent

CONFIDENTIAL

This material is the property of the University of Pennsylvania. Do not disclose or use except as authorized in writing by the study sponsor

and telephone Consent Discussion will not be required to complete a BrAc reading for the safety of the participant and the staff members due to the risk of exposure to COVID-19. Further, a BrAc reading is unnecessary in this case because the participant would have consented at a different time prior to coming into the center for their Intake Visit.

4. A positive urine drug screen (UDS) for cocaine, opiates, amphetamines, methamphetamines, phencyclidine (PCP), ecstasy (MDMA), barbiturates, benzodiazepines, methadone, and/or oxycodone at the Intake Visit.

Medical

1. Women who are pregnant, breast feeding, or planning a pregnancy over the duration of the study period. Women must agree to use an adequate form of contraception or abstain from sexual intercourse for the duration and for at least one month after the end of the study.
2. Current treatment of cancer or diagnosed with cancer (except basal or squamous-cell carcinoma not treated with chemotherapy and/or radiation) in the past 6 months.
3. Poorly controlled, brittle, or pump-dependent Type I diabetes.
4. Current peptic ulcer bleeding.
5. Allergy to adhesive tape.
6. Skin problems or sensitivities. Eligibility will be evaluated on a case-by-case basis by the Study Physician.
7. Active hepatitis or poorly controlled kidney and/or liver disease.
8. Uncontrolled hypertension (systolic blood pressure [SBP] greater than 159 and/or diastolic blood pressure [DBP] greater than 99; see Blood Pressure Procedures under Screening/Covariates).
9. History of abnormal heart rhythms, tachycardia, and/or cardiovascular disease (e.g. stroke, angina, heart attack) may result in ineligibility. These conditions will be evaluated on a case-by-case basis by the Study Physician.
10. History of epilepsy or seizures. Eligibility will be evaluated on a case-by-case basis by the Study Physician.
11. Serious or unstable disease within the past 6 months. Notable diseases will be evaluated on a case-by-case basis by the Principal Investigator and/or the Study Physician.
12. Any impairment including, but not limited to, visual, physical, and/or neurological impairments preventing proper completion of the study procedures. Notable impairments will be evaluated on a case-by-case basis by the Principal Investigator and/or the Study Physician.
13. Low or borderline intellectual functioning – determined by receiving a score of less than 75 on the Shipley Institute of Living Scale (SILS), which correlates with the Wechsler Adult Intelligence Scale-Revised (WAIS-R) Estimated IQ Test.
14. Applicable food allergies or disorders:
 - Galactosemia ^a
 - Notable milk allergy (lactose intolerant participants may proceed unless they experience severe symptoms) ^b
 - Notable soy allergy ^c
 - Peanut allergy ^d

^{a,b,c} Boost® Original Very Vanilla Nutritional Shake: Contains milk and soy ingredients. Suitable for Lactose Intolerance.

^{a,b,c,d} M&M's® (Milk Chocolate): Contains milk and soy ingredients (MAY CONTAIN PEANUTS)

Lay's® Classic Potato Chips (Gluten Free): Potatoes, vegetable oil, and salt

Psychiatric

CONFIDENTIAL

This material is the property of the University of Pennsylvania. Do not disclose or use except as authorized in writing by the study sponsor

1. Current diagnosis of major depression. Subjects with a history of major depression, in remission for 6 months or longer (may be stable on antidepressant medications), are eligible.
2. Lifetime history of a suicide attempt.
3. Lifetime history of schizophrenia, psychosis, and/or bipolar disorder.

Medication

Current use or recent discontinuation (within the last 14 days) of:

1. Smoking cessation medication (e.g., Zyban, Wellbutrin, Wellbutrin SR, Chantix).
2. Anti-psychotic medications.
3. Prescription stimulants (e.g., Provigil, Ritalin, Adderall).
4. Systemic steroids.

Current use of:

5. Nicotine replacement therapy (NRT).
6. Heart medications such as digoxin, quinidine, and nitroglycerin.

Daily use of:

7. Benzodiazepines and/or Barbiturates.
8. Opiate-containing medications for chronic pain.
9. Inhaled corticosteroids.

Subjects will be instructed to refrain from using any study prohibited drugs/medications (both recreational and prescription) throughout their participation in the study. After final eligibility is confirmed, subjects who report taking contraindicated medication(s) over the course of the study period may only remain eligible if the Study Physician and Principal Investigator determine that the contraindicated medication(s) do/did not significantly impact the study design, data quality, and/or subject safety and welfare. Subjects are permitted to take necessary prescription medications not included within the exclusion list during the study.

General Exclusion

1. Past, current, anticipated, or pending enrollment in another research program over the study period that could potentially impact subject safety, study data, and/or the study design as determined by the Principal Investigator and/or Study Physician.
2. Any medical condition, illness, disorder, adverse event (AE), or concomitant medication that could compromise participant safety or significantly impact study performance as determined by the Principal Investigator and/or Study Physician. Subjects may be deemed ineligible for any of the aforementioned reasons at any point throughout the study, as well as during the initial telephone screen.
3. Significant non-compliance with protocol and/or study design as determined by the Principal Investigator and/or Study Physician. Subjects may be deemed ineligible at any point throughout the study.
4. Subjects failing to complete an in-person Baseline Visit will be excluded (no Principal Investigator determination required).

fMRI Exclusion Criteria

The following fMRI exclusion criteria are only pertinent to the neuroimaging sub-study sample – subjects who are not eligible to complete the neuroimaging sub-study may still complete the parent study if appropriate per protocol:

1. History of claustrophobia.
2. Being left-handed.
3. Lifetime history of stroke.
4. Having a cochlear implant or wearing bilateral hearing aids.

CONFIDENTIAL

This material is the property of the University of Pennsylvania. Do not disclose or use except as authorized in writing by the study sponsor

5. History of notable head trauma. Although notable head trauma is typically defined as being knocked unconscious for a period of three minutes or longer, notable head trauma will be evaluated on a case-by-case basis by the appropriate personnel prior to an eligibility decision considering exceptions can be made based on the nature and severity of the trauma.
6. History of brain or spinal tumor.
7. Pacemakers, certain metallic implants or objects, or presence of metal in the eye as contraindicated for MRI.
8. Any circumstances (e.g., exclusionary metal implants, certain dental work, and/or physical impairments) and/or conditions that may interfere with MRI and MRI-related study visit procedures. All potential exclusionary circumstances and/or conditions will be evaluated on a case-by-case basis by the appropriate personnel prior to an eligibility decision.
9. History of gunshot wounds. Injuries from BB guns will be evaluated on a case-by-case basis by the appropriate personnel prior to an eligibility decision.
10. History of epilepsy and/or recurrent or uncontrolled seizures.
11. Weight greater than 250 lbs at Intake Visit or self-reported at phone screen. If a participant weighs less than or equal to 250 lbs at Intake, but presents with a weight greater than 250 lbs at either Scan 1 and/or Scan 2, the participant may be permitted to proceed with the scan as long as the participant's weight does not exceed 300 lbs.
12. A positive urine drug screen (UDS) for cocaine, opiates, amphetamines, methamphetamines, phencyclidine (PCP), ecstasy (MDMA), barbiturates, benzodiazepines, methadone, and/or oxycodone at either Scan Visit. Depending on the substance and circumstances, a subject may be deemed ineligible for the main study at the discretion of the Principal Investigator as well.
13. A BrAC greater than 0.010 at either Scan Visit. Depending on the circumstances, the Principal Investigator may permit the participant to remain in the sub-study and reschedule a neuroimaging scan to another day.

Microbiome Sub-Study Exclusion Criteria

The following exclusion criteria only pertain to inclusion within the microbiome sub-study. Subjects who are not eligible to participate the microbiome sub-study may still complete the parent study if appropriate per protocol.

Current use or recent discontinuation (within the last 21 days) of the following medications:

1. Antibiotics (topical antibiotics are permissible)
2. Antifungals (topical antifungals are permissible)
3. Antivirals (topical antivirals are permissible)
4. Psychotropics

Once a participant is confirmed as eligible for the microbiome sub-study at the Intake Visit, they may remain enrolled in the sub-study even if they report the use of sub-study exclusionary medications listed above. This caveat is in recognition that the impact of certain medications may be unknown until the completion of analyses.

4.7 Vulnerable Populations

Children, pregnant women, fetuses, neonates, or prisoners are not included in this research study. Educationally or economically disadvantaged persons are included but not solely targeted for recruitment. Because of our recruitment efforts for this study, it is possible that University of Pennsylvania employees and students may be invited to participate. Status of participation in the current study will be independent of the participant's work or school activities.

CONFIDENTIAL

This material is the property of the University of Pennsylvania. Do not disclose or use except as authorized in writing by the study sponsor

4.8 Subject Recruitment

Participants may be recruited from television, radio, internet advertisements, social media, newspaper, flyers, transit posters, referrals, and/or from our database of previous participants who have agreed to be re-contacted for future studies. All advertising materials will be submitted to the UPENN IRB for approval prior to distribution/posting. Interested participants will first complete a telephone screen to assess their initial eligibility. Participants who are initially eligible will be screened against our registration database to confirm that they are not currently participating in another research study at our Center and have not previously reported a condition or circumstance that would make them ineligible for the current study. **If the PI deems it is safe for the participant and research staff, based upon federal and University COVID-19 guidance**, then eligible research participants will be invited to the center to complete an Intake Visit during which they will be presented with the IRB approved Informed Consent Form in-person and have their final eligibility confirmed.

Prior to the Principle Investigator's approval, those participants who remain initially eligible at phone screen will then be invited to review the entire IRB approved Informed Consent Form virtually via REDCap to minimize the participants time spend in the research center during the COVID-19 pandemic. After reviewing the IRB approved Informed Consent Form, the participant will complete a telephone Consent Discussion with a member of the research staff. After the participant has had the opportunity to have their questions answered, signed the consent, and agreed to participate, the participant will complete a Shipley Institute of Living Scale (SILS) virtually via REDCap. Participants whose estimated IQ is 75 according to the WAIS-R conversion based upon the exam will be deemed Ineligible per the Exclusion Criteria above. Participants whose WAIS-R estimated IQ is at least a 75 based upon the Shipley will then be invited to the center to have their final eligibility confirmed at an Intake Visit. Early Withdrawal of Subjects

4.8.1 When and How to Withdraw Subjects

Subjects are free to withdraw from the study at any time. Subjects may be deemed "ineligible" at any time per the exclusion criteria listed in section 4.5. No follow-up data collection is required for participants who withdraw or are deemed ineligible throughout the study.

5 Study Drug (Transdermal Nicotine [TN])

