6.2.12 Follow-Up Visits 1 and 2 (Week 12 and Week 26)

During Follow-Up Visits 1 and 2 (Duration: ~30 minutes) participants will:

1. Perform a CO breath assessment or provide a urine sample for a cotinine assessment, answer combustible marijuana items, and complete a concomitant medication review.
2. Provide daily smoking rate (timeline follow back [TLFB]).
3. Have weight measured.
4. Complete paper and pencil questionnaires:
 - Adverse Events Form (Open-Ended AEs)
 - Physical Activity (PAR)
5. If a participant reports not smoking (not even a puff of a cigarette) for at least the 7 days prior to the Follow-Up Visit without the aid of NRT, the participant will be asked to provide a 5ml saliva sample used to assess cotinine levels and verify abstinence from smoking.
6. Confirm the 24-hour dietary recall (Week 12 [#4] and Week 26 [#5]) schedule.

6.2.13 fMRI Scan Visits 1 & 2 (~Week -2 and ~Week 7-8)

Participants who are both eligible and elect to participate in the neuroimaging sub-study will complete two neuroimaging sessions: Scan 1 will occur prior to the Baseline Visit (~week -2) and Scan 2 will occur during the final week of nicotine patch therapy (~week 7-8). Prior to each scan, participants will be instructed to fast overnight (beginning at ~10pm) until after the

CONFIDENTIAL

This material is the property of the University of Pennsylvania. Do not disclose or use except as authorized in writing by the study sponsor

completion of their fMRI scanning visit the following day. The fast period does not include a Boost® Nutritional Drink (Vanilla) that will be provided during the scanning visit to standardize prior food intake and remove deprivation to increase sensitivity to changes in food reward. Since participants are asked to fast overnight, all scanning sessions will be scheduled to occur in the morning. However, a scan may be completed in the afternoon at the discretion of the Principal Investigator due to extenuating circumstances. Additionally, participants will be instructed not to consume caffeine for 4 hours prior to the beginning of the visit in order to standardize satiety. Including the 1-hour fMRI scan, scanning visits are expected to last ~3 hours in duration. If a scanner hardware/software malfunction occurs and data is unable to be collected, an fMRI scan(s) may be rescheduled at the discretion of the Principal Investigator.

At both scanning visits participants will:

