preliminary analyses. Comparisons are all between-subjects. We will test for interaction between treatment and time point using the Wald Chi-square, and estimate a common odds-ratio across time points if they show no evidence of differing across time. The primary hypothesis will be tested using the z-score corresponding to treatment assignment at EOT, and at 12- and 26-weeks post quit, with the primary test of hypothesis 1a at 26-weeks post-TQD. Consistent with ITT analyses, we will measure smoking cessation and weight gain in the full sample at the 26-week follow-up, evaluating a smoking status (days x rate) by treatment interaction for the PCWG analysis (H.1.b.). The **exploratory aim** will evaluate variables that modify the effect of treatment on smoking cessation and PCWG. We will enter interaction terms (e.g., treatment x depression) to the models generated for Aim 1. The interactions will be retained if the z-score is significant ($p<0.05$). We will focus first on EOT, then the 12-week and 26-week follow-up time points, and finally the combined effect across time point.

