9.3 Data Processing

The data entry screens will resemble the data collection forms as closely as possible to allow visual referencing during data entry. This data entry module will be configured for single data entry. Participant data will be collected by research staff, recorded on study-specific CRFs, and scanned in or entered directly into the appropriate DMS module. Data entry checks will be included in the entry screen designs where appropriate to limit the opportunity for erroneous entries due to mistyping. Such data entry checks would include value range comparisons, valid data type checks, required value checks, and/or skip pattern enforcement. Following telephone eligibility screening, research staff will perform subject registration. Following the Intake Visit, research staff will randomize eligible subjects. The randomization module will allow the research staff to randomize subjects into one of the two trial arms. At the randomization attempt, the DMS will check the eligibility data to confirm that randomization is valid. A randomization assignment will then be provided.

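### Section 4.8.1 requires no follow-up data from randomised participants later deemed ineligible, so their week-26 weight, a co-primary outcome, is not secured

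*Combined protocol and SAP*

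**What the plan says.** **Order of events.** Section 9.3: "Following the Intake Visit, research staff will randomize eligible subjects". The Baseline Visit and the first counselling session come after that (6.2.3).

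**Routes to removal after randomisation (4.6).** For a medical condition, adverse event or concomitant medication that could compromise safety or study performance: "Subjects may be deemed ineligible for any of the aforementioned reasons at any point throughout the study". A separate ground is "Significant non-compliance with protocol and/or study design as determined by the Principal Investigator and/or Study Physician", also at any time. After a positive drug screen at a scan visit in the neuroimaging sub-study, "a subject may be deemed ineligible for the main study at the discretion of the Principal Investigator as well"; Scan 2 falls in the last week of patch treatment (6.2.13). Missing the in-person Baseline Visit leads to automatic exclusion.

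**Data after removal (4.8.1).** "No follow-up data collection is required for participants who withdraw or are deemed ineligible throughout the study". This section points to 4.5 for the exclusion criteria, which stand in 4.6.

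**What the analysis expects.** Section 6.10: "Consistent with ITT analyses, we will measure smoking cessation and weight gain in the full sample at the 26-week follow-up". Section 3.1 says the same, and 6.7 puts all participants into the weight-gain analysis. Section 6.5.6 makes weight change from Baseline to week 26 a primary outcome.

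**Handling of missing outcomes.** Section 4.2 counts smokers lost to follow-up as smokers. Section 6.10 plans to compare attrition across arms. It leaves the missing-data method to be chosen once the extent and type of missingness are known, with multiple imputation and all available data as examples.

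**The concern.** An intention-to-treat comparison needs outcomes on people as randomised, including those who later leave the programme. Here staff may end participation for reasons that arise after allocation, and the protocol then places no duty on anyone to obtain the week-26 weight.

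Some of these reasons could be related to the arm. BAS+ adds daily activity monitoring and activity goals to standard counselling, so non-compliance might arise or be judged differently in the two arms. The documents do not say that removal decisions are made without knowledge of the arm. This is a possibility, not something the documents show.

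If the missing weights differ systematically from those seen, the estimated effect on a co-primary outcome depends on assumptions that the collected data cannot test.

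**Working it through.** The point is procedural, and the plan gives no figure for it, so the check sets the passages side by side.

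1. **Can removal follow randomisation?** Yes. Allocation comes after Intake (9.3), and the removal grounds in 4.6 apply throughout the study.

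2. **Is week-26 weight obtained after removal?** Not by requirement. Section 4.8.1 waives outcome follow-up. The follow-up that continues under section 8 concerns adverse events, not outcomes.

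3. **Does another rule supply the outcome?**
   - Abstinence: largely, if removed participants are treated as lost to follow-up under 4.2. That rule does not name them.
   - Weight: no. Counting someone as a smoker gives no weight. Nor does it give the days-by-rate smoking measure that 6.10 uses in the interaction term of the weight analysis.

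4. **Do the planned analyses recover it?** Only in part. Weight is taken at every in-person visit (6.5.6), and the longitudinal model in 6.10 can use those earlier values, which helps most for people removed late. The attrition comparison can reveal an imbalance but returns no weights. The 15% attrition estimate in 6.7 enlarges recruitment, so it addresses precision and not bias.

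5. **Which removals matter most?** Those excluded for missing Baseline have had no assigned counselling, so their exclusion cannot reflect response to it. The concern is mainly with later removals.

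**Illustration only.** The documents give no removal rate, so every input below is an assumption. Let a share m of week-26 weights be missing in each arm, let only observed weights be used, and let the between-arm difference among the unseen depart from the observed difference by D kg. Then

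full-sample difference = (1 − m) × observed + m × (observed + D) = observed + m × D.

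| m | D = 1 kg | D = 2 kg | D = 2.72 kg |
|---|---|---|---|
| 5% | 0.05 | 0.10 | 0.14 |
| 10% | 0.10 | 0.20 | 0.27 |
| 15% | 0.15 | 0.30 | 0.41 |

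The entries are shifts in kg. The 2.72 kg is the difference that 6.7 aims to detect through the interaction term and serves here only as a yardstick. The 15% row borrows the all-cause attrition estimate, which does not measure removals by staff.

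**The case against.** Several stronger readings are tempting, and the documents do not support them.

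- *A reader might infer that outcomes will not be collected after removal.* Section 4.8.1 says only that collection is not required; it does not forbid it.
- *A reader might infer a flat contradiction with intention to treat.* In 3.1 and 6.10 the full sample is mentioned together with the smoking-status-by-treatment interaction, and 6.7 contrasts with an exploratory analysis restricted to abstainers. The phrase may mainly mean smokers as well as abstainers. Even so, no passage secures a week-26 weight for those removed.
- *A reader might infer that an adverse event, a contraindicated medication or a missed visit generally ends participation.* It need not. Participants who stop the patch for a medical event may continue (6.5.1), and those who fail the Pre-Quit blood pressure check may still receive counselling (6.5.2). Contraindicated medication can be judged compatible with remaining (4.6), and visits after Baseline can be covered by telephone (3.1). The group at issue is narrower than the list of grounds suggests.
- *A reader might infer that both primary outcomes are exposed alike.* Abstinence is largely covered by the rule in 4.2.
- *A reader might take the plan's attrition or accrual figures as the number removed.* They cover all causes or describe recruitment targets.

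Two practical objections stand. People removed for non-compliance may not attend when asked, so asking reduces missing weights but does not abolish them. Timing also counts: 3.4 has enrolment starting in September 2016 for about 44 months, with completion expected by December 2020, and this version contains pandemic-era procedures. On those dates many week-26 windows had probably closed.

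**Conclusion.** The point holds in a limited form. For randomised participants whom staff later deem ineligible, the protocol does not secure week-26 weight, and neither the smoker rule, the attrition comparison nor the open choice of missing-data method replaces it. Earlier weights and the longitudinal model lessen the loss, under assumptions about the unseen values.

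The number of participants affected and the direction and size of any bias cannot be stated from the documents. The illustrative shifts rest on assumed shares and differences and are not estimates. This is an inexpensive improvement to the protocol. It does not show that the weight comparison is biased.

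**What to change.** Amend 4.8.1 as follows. This changes data collection and analysis only, not who is removed or how anyone is treated.

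- Randomised participants removed by staff are still asked for smoking status and weight at the existing week-12 and week-26 visits, unless they withdraw consent to follow-up.
- They stay in the ITT set in their assigned arm. Those without smoking data are counted as smokers under 4.2.
- Weights after a removal for pregnancy (7.1, Reproductive Risks) are treated as missing for the weight outcome, because they would not measure post-cessation gain.
- Date and reason of removal, by arm, are added to the attrition comparison already planned in 6.10.

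**Cost.** Protocol wording, plus two visits of about 30 minutes (6.2.12) for each removed participant: 2 × 30 minutes = about 1 hour. Table 3 pays $50 per visit including travel: 2 × $50 = $100. Add the effort of making contact and a saliva cotinine sample from those reporting abstinence.

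The change to follow-up helps only participants whose windows are still open. For the rest, the ITT statement and the report of removals by arm are what remains.
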